9.3 WITHDRAWAL OF SUBJECTS

Participants can leave the study at any time without giving any specific reason but will be followed-up for safety reasons.

The Investigator can decide to withdraw a participants from a study treatment. If this decision is made because of a serious adverse event (SAE) related to the study medication, the treatment is discontinued and appropriate measures are taken. The participants will continue follow-up according to the protocol.

In case of written withdrawal of consent for follow-up visits and unless otherwise stated by the participants, the Investigator will be encouraged to follow the medical status of the patients.

The Sponsor should be notified immediately (within 24 hrs) about participants withdrawals due to Serious Adverse Events. The reason for the study discontinuation will be recorded in the CRF.

Specific criteria for withdrawal are:

- AE that precludes further continuation of treatment
- No compliance with study procedures
- The patient becomes pregnant
- Other medical reason according to the Investigator
- Patient's decision

Participants, who are withdrawn from the study will receive medical care according to local practice. In case of withdrawal due to an AE, participants will be closely monitored until resolution or stabilization of this AE. This may mean that follow-up will continue due to safety reasons.

Participants, who are not eligible for the study because in hindsight they were not eligible for the study, will continue to follow the study schedule.

For participants considered lost to follow-up, the CRF must be completed up to the last visit performed.

9.4 SUBJECT LOG AND SCREENING OF SUBJECTS

Participants will receive a consecutive screening number when signing the informed consent and are thereafter considered to be enrolled in the study.

It is the responsibility of the Investigator that all participants that have signed Informed Consent are listed on the "Screening and enrolment log". The reason for rejecting a participants before first treatment should be specified in the comment field of the log.

If the participant is eligible, he/she will receive a randomization number and the study drug bottle with the same randomization number will be distributed to the patient and the parents/guardians. It is the responsibility of the investigator to keep a patient identification log, identifying the individual behind each randomization number.

The Subject Enrolment and Identification log contains information to enable identification of each participant. It is included in the Investigator's File and shall be kept by the Principal Investigator in a safe place.

The participants will have the same randomization number through the study and this number will not be reused in case the participant is withdrawn from the study.

10 TREATMENT OF SUBJECTS

10.1 TREATMENT ADMINISTRATION

The intervention is treatment with either prednisolone (capsule Prednisolone 5 mg), 1 mg/kg once daily in 10 days or control treatment (capsule placebo) once daily in 10 days. The number of capsules is based on the child's weight pre-calculated in table 2. The dosage choice is based on results from earlier studies on prednisolone treatment, and a clear schedule (same dosage once daily in 10 days) will make a good compliance possible.

The specific child's dosage will be given to parents/guardians and noted in CRF. If the child has problems to swallow the capsules, they may be opened and the content can be mixed with a small amount (about one tablespoon) of something tasty in order to facilitate per oral administration and to ascertain the intake of the child's dosage of the study medication.

Table 2. Dosage of prednisolone/placebo. Treatment period is 10 days, maximum dosage is 50 mg per day.

Child's weight /kg	Number of capsules/day	Total number of capsules
5 - 9.9	2	20
10 - 14,9	3	30
15 - 19.9	4	40
20 - 24.9	5	50
25 - 29.9	6	60
30 - 34.9	7	70
35 - 39.9	8	80
40 - 44.9	9	90
>45	10	100

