	disorder, active or latent tuberculosis, intolerance of lactose)
5.	Current or past oncological diagnosis
6.	Other serious medical conditions (meningitis, encephalitis, stroke)
7.	Acute otitis media
	Signs of herpes simplex or varicella zoster infection (vesicles in the ear region)
9.	Pregnancy or breastfeeding
	Use of any systemic or inhaled steroids within 2 weeks prior onset of symptoms
	Immunization with live vaccine 1 month prior onset of symptoms
12.	Requirement of live vaccine within 2 months from start of experimental treatment (prednisolone or placebo)
13	Evaluation of primary endpoint at 12 not feasible for any reason
	Previously included into the FACE study
vestig	ational product, dosage and mode of administration:
edniso	olone capsules 5 mg, dosage 1 mg/kg body weight (maximum 50 mg) x 1, per oral
iratio	n of treatment:
days	
·	control, dosage and mode of administration:
	capsules, same number of capsules as investigational product for each child, maximum 10 capsules x 1,
r oral	capsules, same number of capsules as investigational product for each child, maximum 10 capsules x 1,
i oral	

SYNOPSIS

Primary Endpoint:

The total recovery rate at 12 months follow-up in the two treatment groups measured with the House-Brackmann scale.

Secondary Endpoints:

The total recovery rate at 12 months follow-up in the two treatment groups measured with the Sunnybrook scale.

The total recovery rate at 1 month follow-up as compared to the total recovery rate at 12 months follow-up, measured with Sunnybrook and House-Brackmann scale (prediction).

Quality of daily life at 1 and 12 months follow-up measured with the Facial Clinimetric Evaluation (FaCE) scale and the Facial Disability Index (FDI) and at the 12 months follow-up measured with the Synkinesis Assessment Questionnaire (SAQ).

Number of Adverse Events possibly or probably related to the study drug during the 12 months follow-up.

Statistical methods:

Intention-to-treat will be applied when analyzing results from the primary outcome.

Comparisons between groups for dichotomous endpoints (recovery/no recovery) will be performed using Fisher's exact test and for categorical endpoints (scale) using Mann-Whitney U-test. For correlations between scales, Pearson's correlation test, or Cohen's kappa if appropriate, will be used.

When predicting recovery at 1 month to 12 months, diagnostic performance will be calculated on total recovery defined as House-Brackmann grade 1.

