10.2 DESCRIPTION OF INVESTIGATIONAL PRODUCTS

Capsule Prednisolon 5 mg (APL), dosage 1 mg/kg (max 50 mg) once daily for 10 days according to pre-calculated weight table (Table 2). All bottles include 100 capsules.

Capsule Placebo (APL), dosage once daily equivalent to 1 mg/kg (max 10 capsules) for 10 days according to pre-calculated weight table (Table 2). All bottles include 100 capsules.

See separate product information and pharmacological documents from APL for prednisolone and placebo.

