16.2 RISK - BENEFITS

A risk analysis for this study has been made. These risks together with the actions to minimize these risks are compiled below:

	Anticipated risk	Action
1	Side effects such as minor behavior problems (mood changes), sleep disturbances, nausea or vomiting	Reported as Adverse Events and follow up until recovered. A Development Safety Update Report (DSUR) will be presented yearly to MPA
2	Trauma for the child to take medicine	Capsules may be opened and the content can be mixed with something tasty. The study nurse will instruct the parents/guardians when study medication is distributed and will also follow up how it works by telephone calls one and two weeks after Baseline
3	No effect on the recovery rate	There is no alternative treatment, why there is no risk that the patient looses an effective treatment by participating in the study

A short-course oral treatment with corticosteroids (defined as 1-2 mg/kg once daily in 7-14 days) is not associated with major side effects, such as risk of growth retardation, osteoporosis or diabetes mellitus in children, but may be associated with minor side effects, such as behavioral problems (mood changes), sleeping disturbances, nauseas or vomiting in 4,3 – 5,4 % of cases (17,25,26).

The risk of minor side effects will be reduced with the dose $1 \text{ mg/kg} \times 1$ (17), as we plan on using in the present study.

Increased susceptibility to infection (<1%) is the most frequent (S)AEs associated with short courses of corticosteroids (25,26). In five large RCTs on short-course corticosteroid treatment, three children with varicella infection needed intensive care due to complications (25).

Parents/guardians will be informed before start of treatment in the current study about the importance to attend health care if fever or signs of infection occur during the study period.

In summary, the benefits, i.e. possibly improved recovery of the facial nerve palsy are anticipated being higher than the risks.

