### Intervention:

Prednisolone 1 mg/kg (max 50 mg) per orally once daily in 10 days, given as 5 mg capsules (blinded) based on weight intervals (5 kg) up to > 50 kg.

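### The capsule table assigns more than the stated 1 mg/kg at every listed weight below 50 kg without saying so, and SAP section 6 disagrees with both tables on the top weight band

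*Protocol*

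**What the plan says.** The stated dose is the same throughout. The protocol synopsis gives "dosage 1 mg/kg body weight (maximum 50 mg) x 1, per oral". Protocol 10.1 gives "prednisolone (capsule Prednisolone 5 mg), 1 mg/kg once daily in 10 days" and, under Table 2, adds "Treatment period is 10 days, maximum dosage is 50 mg per day". SAP sections 6 and 8.3 also state 1 mg/kg with a 50 mg maximum.

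The number of capsules comes from a table. Protocol 10.1: "The number of capsules is based on the child's weight pre-calculated in table 2". Protocol 10.2 presents the table as the way the stated dose is given: "dosage 1 mg/kg (max 50 mg) once daily for 10 days according to pre-calculated weight table (Table 2"). SAP 8.3 reprints it with the same bands and counts. Both tables start at 5 kg with 2 capsules, add one capsule per 5 kg band, and end with a band above 45 kg at 10 capsules.

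SAP section 6 describes the bands differently: "based on weight intervals (5 kg) up to > 50 kg".

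Protocol 16.2 relies on the stated figure: "The risk of minor side effects will be reduced with the dose" of 1 mg/kg once daily, which it says is the dose planned here. The same section describes the short courses it assesses as 1-2 mg/kg once daily for 7-14 days.

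**The concern.** A table that implements 1 mg/kg should scatter around that figure or, if it is meant to lie on one side, say so. Table 2 lies above it at every listed weight below 50 kg. A child of 10 kg needs exactly 2 capsules for 1 mg/kg and is assigned 3; a child of 20 kg needs exactly 4 and is assigned 5.

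Three things depend on this:

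- **The label on the result.** Protocol 5.1 says that a beneficial result will lead to clinical use and international guidelines. Readers would take 1 mg/kg as the dose tested.
- **The sentence in Protocol 16.2** that attributes fewer minor side effects to 1 mg/kg.
- **Interpretation by age.** Dose per kg varies with weight, and so broadly with age. SAP 8.9 puts age group into the logistic regression for 12-month recovery, but no summary of mg/kg is planned. SAP 8.3 covers only percentage compliance.

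Separately, the documents do not agree on where the top band begins, and one exact weight is left unassigned.

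**Working it through.** **Inputs.** Capsule strength 5 mg (Protocol 10.1). Bands and counts from Protocol Table 2, identical in SAP 8.3. Stated dose 1 mg/kg, maximum 50 mg.

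**Figures that reproduce.** Total capsules = daily count × 10 days (2 × 10 = 20, up to 10 × 10 = 100). Maximum daily dose = 10 × 5 mg = 50 mg. Both agree with the table.

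**The figure that does not.** Assigned mg/kg = capsules × 5 / weight.

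| Weight (kg) | Capsules | mg/day | mg/kg at lower edge | mg/kg at midpoint | mg/kg at upper edge |
|---|---|---|---|---|---|
| 5-9.9 | 2 | 10 | 2.00 | 1.34 | 1.01 |
| 10-14.9 | 3 | 15 | 1.50 | 1.20 | 1.01 |
| 15-19.9 | 4 | 20 | 1.33 | 1.15 | 1.01 |
| 20-24.9 | 5 | 25 | 1.25 | 1.11 | 1.00 |
| 25-29.9 | 6 | 30 | 1.20 | 1.09 | 1.00 |
| 30-34.9 | 7 | 35 | 1.17 | 1.08 | 1.00 |
| 35-39.9 | 8 | 40 | 1.14 | 1.07 | 1.00 |
| 40-44.9 | 9 | 45 | 1.13 | 1.06 | 1.00 |
| >45 | 10 | 50 | 1.11 (at 45.1 kg) | – | 1.00 (at 50 kg) |

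The upper-edge entries shown as 1.00 for the bands from 20 to 44.9 kg are 1.002 to 1.004 before rounding, so still above 1. In the last band, 49.9 kg gives 50 / 49.9 = 1.002 and 50 kg gives exactly 1.00. Beyond that the cap lowers the ratio: 50 / 60 = 0.83 and 50 / 70 = 0.71.

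**Which rule the table follows.** Candidate rules were compared with the table on a 0.1 kg grid from 5.0 to 49.9 kg (450 weights, counting 45.0 kg with the top band):

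- nearest whole capsule: agrees at 50% of weights
- round down: 0%
- round up: 98%
- floor(weight / 5) + 1: 100%

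The last two rules differ only at exact multiples of 5 kg (9 of 450 weights, 2%), where the table adds one capsule beyond the exact dose.

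**Average size.** If weights were spread evenly over 10-50 kg, which is an assumption, the mean of 5 × (floor(w/5) + 1) / w is about 1.10 mg/kg. Over 10-20 kg it is about 1.18. The documents give no weight distribution, and these averages leave out children above 50 kg.

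**Largest excess.** From 5 kg it is 10 / 5 = 2.00 mg/kg (+100%). It is above 50% only for weights below 10 / 1.5 = 6.67 kg; from there upward the maximum is +50%, reached again at 10 kg. No lower weight limit is set. How many children under 10 kg would enter from age 1 year is not known from the documents.

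**Band edges.** The tables run 40-44.9 and then >45, so exactly 45.0 kg has no entry. The neighbouring bands would give 9 × 5 / 45 = 1.00 or 10 × 5 / 45 = 1.11 mg/kg. SAP section 6 gives no capsule count for its band above 50 kg, so it cannot be told whether it implies different counts between 45 and 50 kg.

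**The case against.** The strongest reply is that the table is itself part of the described regimen. Protocol 10.2 defines the dose by reference to it, SAP 8.3 reprints it, and 1 mg/kg is only the nominal name for a banded, whole-capsule scheme. This largely stands. A reader might infer a hidden regimen, or an intervention other than the one approved; the documents do not support that, because the counts are printed and the two tables agree. What remains is that neither document says the scheme goes above the stated figure or by how much.

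Second, rounding up to whole capsules explains almost all of the table. That also stands, apart from exact multiples of 5 kg. It explains the pattern but does not disclose it.

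Third, Protocol 16.2 assesses courses of 1-2 mg/kg, and no listed weight exceeds 2.00 mg/kg. A reader might infer a safety problem from the 5 kg or 10 kg figures; the documents do not show one. Only the single sentence tied to 1 mg/kg is affected.

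Fourth, both arms use the same table, so the comparison, type I error and sample size are untouched. This stands in full.

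Fifth, age enters SAP 8.9 as a predictor of recovery, while the treatment comparison by subgroup is by idiopathic or *Borrelia*-associated palsy. So the age argument supports a descriptive summary and no more.

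Last, the 45.0 kg gap concerns one weight and may be typographical. Both documents print the same sign, so it still needs settling.

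**Conclusion.** The point holds as a mismatch between the stated dose and the table that implements it. Below 50 kg every listed weight is assigned more than 1 mg/kg: between 0.2% and 50% more from 10 kg upward, and up to 100% more at the 5 kg edge. The average is about 10% more if weights are even over 10-50 kg. The band edges and ratios need no assumption beyond the 5 mg capsule; the averages rest on the even spread.

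Two further readings go too far. One is that all children are assigned more than 1 mg/kg: at 50 kg the dose is exact, above 50 kg the cap takes it below, and eligibility runs to 17 years. The other is that dose per kg falls steadily with size: only the band maxima do, and within bands the pattern is a sawtooth (1.01 at 9.9 kg, 1.25 at 20 kg).

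The band conflict is between the text of SAP section 6 and the two tables, not between the tables. The consequence is for description and reporting, not for the validity of the randomized comparison. It should be corrected because the trial's conclusion and a risk-benefit sentence both use the 1 mg/kg figure.

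**What to change.** Reconcile the synopsis, Protocol 10.1, 10.2, Table 2 and 16.2 with SAP sections 6 and 8.3, so that four things agree: the stated dose, the capsule table, the start of the top weight band, and the entry for exactly 45.0 kg. Which of the conflicting statements is right is for the sponsor to settle; this review does not propose a dose or a band. The reconciled text should state the mg/kg range that the table produces.

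Add to SAP 8.3 one descriptive table of assigned mg/kg (capsules per day × 5 / baseline weight; for placebo, the equivalent from the capsule count) by arm and by the age groups in SAP 8.9, and report the result with that range.

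The cost is wording in both documents, under the amendment procedure of Protocol 20.1 where it applies, and one table. Weight is already collected at baseline and each child's dosage is already noted in the CRF, so no new data are needed.

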10.2 DESCRIPTION OF INVESTIGATIONAL PRODUCTS

Capsule Prednisolon 5 mg (APL), dosage 1 mg/kg (max 50 mg) once daily for 10 days according to pre-calculated weight table (Table 2). All bottles include 100 capsules.

Capsule Placebo (APL), dosage once daily equivalent to 1 mg/kg (max 10 capsules) for 10 days according to pre-calculated weight table (Table 2). All bottles include 100 capsules.

See separate product information and pharmacological documents from APL for prednisolone and placebo.

10.3 PACKAGING AND LABELING OF INVESTIGATIONAL PRODUCTS

The study medication (prednisolone and placebo capsules) will be put in bottles and labelled with a unique study code according to randomization list (prepared by the statistician at UCR) at APL, and then sent to Tamro AB for distribution to study centers.

The bottles of study medication will be given to the patients/guardians at the screening/baseline visit after informed consent has been signed and eligibility for participation is confirmed by the Investigator.

10.4 STORAGE AND HANDLING

The study medication can be stored in room temperature. The medication can be placed at the local pharmacy or in a locked cabinet or room for medical products at the clinic.

10.5 RANDOMIZATION AND BLINDING

Randomization is repared by the study statistician at UCR. A randomization list using variable block sizes will be used and applied when undertaking blinding, coding and labeling the study medication (prednisolone or placebo).

The study drugs (prednisolone or placebo) will be labeled with the randomization code at APL, and then sent to Tamro AB for further distribution to the different study centers.

The code envelopes for unblinding will be kept at each study center. In case the code has to be broken due to an emergency situation, the Coordinating Investigator ([name]) will be contacted, see also details in section 12.8.

10.6 CONCOMITANT THERAPY

Children with *Borrelia* associated acute facial nerve palsy will receive antibiotic treatment according to national guidelines, i.e. ceftriaxone 50-100 mg/kg x 1 in 10-14 days (1-7 years of age), or doxycycline 4 mg/kg x 1 in 10-14 days, or 200 mg x 1 first day and then 100 mg x 1 in 10-14 days (5).

If other concomitant medications permitted in the study are taken, they will be listed in the CRF. Data registered are generic/trade name, dosage, start and end date of the medication, and indication.

Use of any systemic or inhaled steroids within 2 weeks prior to onset of symptoms is not permitted. No live vaccines are permitted during the period one month prior to onset until 2 months after study treatment. For more information about medical conditions not permitted in the study, see Subject Exclusion Criteria, section 9.2.

10.7 COMPLIANCE WITH THE TREATMENT

The study nurse will inform the child/parents on how to administer the study medication (capsules with prednisolone or placebo). If it is not possible for the child to swallow the capsules, there is a possibility to open the capsules and mix the content with something tasteful in order to facilitate compliance.

Telephone calls 1 and 2 weeks after baseline are planned to support the families and the compliance of the study medication and to follow-up if Adverse Events have occurred.

Parents/guardians will be instructed to return the bottles with the remaining study medication for drug accountability check.

10.8 ACCOUNTABILITY OF INVESTIGATIONAL PRODUCTS

Accountability will be measured by counting remaining capsules in the bottles, which should be returned to the study nurse at the pediatric clinic after usage, at the latest at the 1 month follow-up visit.

10.9 CONTINUATION OF TREATMENT

After 10 days treatment stops. No further treatment will replace the study medication.

Concomitant therapy (e.g. antibiotics 10-14 days, se 10.6) will be finished as prescribed by the responsible pediatrician.

11 ASSESSMENT OF EFFICACY

11.1 INVESTIGATOR'S ASSESSMENTS

The Investigators will perform evaluation using the House-Brackmann and Sunnybrook grading scales for facial nerve palsy at the three study visits (screening/baseline, 1 month, 12 months). Education for the study, including written instructions on how to perform the evaluation will be given to the investigators before study start.

11.2 SUBJECT'S ASSESSMENTS

The child and/or parents/guardians will complete the Facial Disability Index (FDI), the Facial Clinimetric Evaluation Scale (FaCE scale) at 1 month and 12 months follow-up and the Synkinesis Assessment Questionnaire (SAQ) at the 12 months follow-up to evaluate their personal subjective experience of the facial nerve palsy.

These questionnaires will be completed by the child/adolescent alone or together with the parents/guardians, which will be optional and documented at the end of each questionnaire.

12 ASSESSMENT OF SAFETY

Safety will be evaluated by recording of routine laboratory tests (white and red blood cells, CRP, electrolytes and glucose), physical examinations, blood pressure and vital signs measurements. Adverse Events (AEs) or Serious Adverse Events (SAEs), will be reported if occurring during the study period (12 months).

Any clinically relevant changes and actions taken, for instance occurrence of an adverse event or administration of concomitant medication, will be recorded in the CRF and hence in the database.

12.1 DEFINITION OF ADVERSE EVENTS

An AE is any untoward medical occurrence that does not necessarily have to have a causal relationship with the investigational product. An AE can be any unfavourable, unintended clinical sign, symptom, medical complaint or clinically relevant change in laboratory variables or clinical tests. Accidents, operations not pre-planned, changes in medication or deterioration in concurrent illness are also considered as AEs.

12.2 METHODS FOR ELICITING, RECORDING AND FOLLOW-UP OF ADVERSE EVENTS

Information regarding AEs is to be obtained by questioning or examining the subject after having signed the ICF. At each visit all new complaints and symptoms (i.e., those not existing prior to signing of informed consent) must be recorded on the AE CRF.

Pre-existing complaints or symptoms that increase in intensity or frequency after having signed the ICF must also be reported as an AE.

All AEs must be characterized in terms of their start and stop dates, maximum intensity, action taken on the study medication, relationship to study medication, subject outcome and whether or not the AE led to a SAE. Any clinically relevant increase or decrease to the intensity or frequency of a reported AE requires a separate entry on the AE form.

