5 BACKGROUND INFORMATION

The annual incidence of acute facial nerve palsy in European pediatric populations are about 5-21/100 000 children (1,2). The facial nerve palsy is often idiopathic, but may be caused by a *Borrelia* infection in the nervous system (2,3). The physiological reason for impairment of the facial nerve is an anatomically tight passage through the bone of the scull and when the nerve becomes swollen, for some reason, the nerve function is impaired and the facial muscles on the ipsilateral side are affected.

In children, *Borrelia* associated facial nerve palsy occurs more often (65%) than *idiopathic* facial nerve palsy (35%) (2). *Borrelia* associated facial nerve palsy is treated with antibiotics according to European guidelines (4,5).

An acute facial nerve palsy, regardless of etiology, may lead to a permanent dysfunction in 20-30 % of the patients, involving problems with tear secretion, drooling and pronunciation in addition to cosmetic and social problems (6-8).

Adult patients with idiopathic acute facial nerve palsy (Bell's palsy) are recommended cortisone treatment in order to improve the recovery rate (9). This recommendation is based on several randomized clinical trials (RCTs) (9,10). Studies on pediatric patients with acute facial nerve palsy and cortisone treatment are scarce and no RCT has been performed (11,12).

There are a few uncontrolled treatment studies on cortisone to children with acute idiopathic facial nerve palsy showing a total recovery rate up to 80-90% (13-16). Prednisolone in a dosage of 1-2 mg/kg daily in 7-14 days has been used in pediatric patients without reported adverse events (15,17).

One protocol has recently been published from New Zealand about a RCT study using prednisolone 1 mg/kg daily in 10 days (with a reduced dose day 7-10) for treatment of children with facial nerve palsy (18). We have in the FACE study chosen prednisolone in a dosage of 1 mg/kg daily in 10 days without taper in order to give a treatment that is easy to follow (compliance) and effective enough to regain function of the facial nerve (efficacy).

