12.5 DEFINITION OF SERIOUS ADVERSE EVENTS

A serious AE is any untoward medical occurrence that at any dose:

- Results in death.
- If life threatening at the time of the event.
- Requires inpatient hospitalisation
- Requires prolongation of existing hospitalisation.
- Results in persistent or significant disability/incapacity.
- Is a congenital anomaly/birth defect.

Medical and scientific judgment should be exercised in deciding whether expedited reporting is appropriate in other situations, such as important medical events that may not be immediately life-threatening or result in death or hospitalization, but may jeopardize the patient or may require intervention to prevent one of the other Protocol version 2.3 2021-06-04

outcomes listed in the definition above. These also should usually be considered serious.

Also serious events which could be associated with the study procedures (rather than with the study medication) will be reported as SAEs, even if occurring outside the treatment period.

Under this protocol, the following events will not be considered as an SAE and should not be entered on the SAE form:

Elective hospital admission

Pre-planned hospitalizations for diagnostic, therapeutic, or surgical procedures for a pre-existing condition that did not worsen during the course of a clinical study. These pre-planned hospitalizations and the underlying conditions must be entered on the medical history form.

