### 8.7. Safety analyses

Adverse events (AEs) will be presented in per-patient data listings and summarized in frequency tables. A summary table will be presented with number of patients with:

- AEs
- serious AEs
- related AEs
- AE leading to discontinuation

for each treatment and in total.

Adverse events (AEs) will be presented in per-patient data listings and summarized in frequency tables by treatment and in total. AEs will be summarized as number of events and number of patients, respectively, by intensity, seriousness and relationship. SAE will be presented in a separate listing.

Safety profile will be evaluated by comparing number (%) of adverse event (AE) and serious adverse events (SEA) in each group. Difference between groups in safety profile will be compared with Chi2-test or when appropriate, Fischer's exact test.

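### SAP 8.7 tests all AEs and SAEs between arms without separating progression and new sequelae of the palsy, so a benefit of prednisolone could dilute a drug-caused AE excess

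*Protocol*

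**What the plan says.** **Recording.** Protocol 12.1 defines an AE without regard to cause and adds that "deterioration in concurrent illness are also considered as AEs". Protocol 12.2 says that at each visit "all new complaints and symptoms (i.e., those not existing prior to signing of informed consent) must be recorded on the AE CRF". It also says: "Pre-existing complaints or symptoms that increase in intensity or frequency after having signed the ICF must also be reported as an AE". Protocol 12 runs AE and SAE collection over the 12-month study period, which ends at the primary-endpoint visit.

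**Seriousness.** One SAE criterion in Protocol 12.5 is "Results in persistent or significant disability/incapacity". The same section lists what is exempt ("the following events will not be considered as an SAE and should not be entered on the SAE form"), and the list holds only elective and pre-planned admissions. The palsy under study is not mentioned.

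**Expected course.** Protocol 5 says that an acute facial palsy "may lead to a permanent dysfunction in 20-30 % of the patients, involving problems with tear secretion, drooling and pronunciation". SAP 9 assumes recovery of 80% on placebo and 90% on prednisolone.

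**Analysis.** SAP 8.7 says: "Safety profile will be evaluated by comparing number (%) of adverse event (AE) and serious adverse events (SEA) in each group". It names the chi-square or Fisher test for the difference between groups. The safety endpoint in Protocol 7.2 and SAP 5.2.3 is narrower: AEs rated possibly or probably drug-related. SAP 8.7 tabulates related AEs by arm but states no between-arm test for them.

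**The concern.** A child enters within 72 hours of onset, so the palsy may still deepen after consent. Synkinesis, tearing or drooling may first appear later. Under the wording of Protocol 12.2 each of these is a new or increased complaint and therefore an AE. These are also events that effective treatment should make rarer.

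The all-AE comparison would then contain two treatment effects of opposite sign: any harm caused by the drug, and the reduction in palsy events that the trial hopes to show. Randomisation and blinding do not remove this, because the imbalance in palsy events is itself an effect of treatment. The safety profile of cortisone is a stated secondary objective, and Protocol 5.1 foresees clinical guidelines if the drug works. That is the case in which the dilution would arise.

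**Working it through.** **1. Which palsy events qualify.** Reading Protocol 12.2 literally:
- deepening of the palsy after consent is a pre-existing complaint that increased, so it is an AE;
- synkinesis, tearing, drooling or speech problems that first appear after consent are new complaints, so they are AEs;
- weakness present at consent that fails to recover is neither new nor worse, so it is not an AE.

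An SAE needs a qualifying event that also meets a seriousness criterion.

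**2. Inputs.**
- Non-recovery 20% on placebo and 10% on prednisolone; 250 per arm (SAP 9).
- Minor side effects of short-course steroids 4.3-5.4% (Protocol 16.2). I take this as h, the drug-caused excess over placebo. That is an assumption, since the protocol gives it as a plain rate.
- c, the share of non-recovered children with a new or worsened palsy complaint logged as an AE. Not in the documents; varied from 0 to 1.
- b, the background share of children with any other AE over 12 months. Not in the documents; 0, 10% and 20% are shown.
- Two-sided 5% chi-square test (SAP 8 and 8.7).

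SAP 9 asks for 430 patients for 80% versus 90% with 80% power. The standard two-proportion formula gives 199 per arm (398) without continuity correction and 219 per arm (438) with it, 1.9% from 430. The sample size is not in dispute.

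**3. Model.** With independent events:
- placebo: P(any AE) = 1 - (1 - b)(1 - 0.20c)
- prednisolone: P(any AE) = 1 - (1 - b)(1 - h)(1 - 0.10c)

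**4. Logging share at which the excess disappears.** Set the two equal. The factor (1 - b) drops out:

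1 - 0.20c = (1 - h)(1 - 0.10c), so c = h / [0.10(1 + h)]

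- h = 4.3%: 0.043 / 0.1043 = 41%
- h = 5.4%: 0.054 / 0.1054 = 51%
- h = 10%, for comparison: 0.10 / 0.110 = 91%

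**5. Smaller shares.** Ranges run from h = 4.3% to h = 5.4%. The last column is the exact binomial probability, at 250 per arm, of a significant excess on prednisolone.

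| b | c | Placebo | Prednisolone | Difference (points) | P(significant excess) |
|---|---|---|---|---|---|
| 0 | 0 | 0% | 4.3-5.4% | +4.3 to +5.4 | 0.995-0.999 |
| 0 | 0.25 | 5.0% | 6.7-7.8% | +1.7 to +2.8 | 0.12-0.24 |
| 0 | 0.50 | 10.0% | 9.1-10.1% | -0.9 to +0.1 | 0.01-0.03 |
| 10% | 0 | 10.0% | 13.9-14.9% | +3.9 to +4.9 | 0.26-0.38 |
| 10% | 0.25 | 14.5% | 16.0-17.0% | +1.5 to +2.5 | 0.07-0.12 |
| 10% | 0.50 | 19.0% | 18.2-19.1% | -0.8 to +0.1 | 0.01-0.03 |
| 20% | 0 | 20.0% | 23.4-24.3% | +3.4 to +4.3 | 0.15-0.21 |
| 20% | 0.25 | 24.0% | 25.4-26.2% | +1.4 to +2.2 | 0.05-0.08 |
| 20% | 0.50 | 28.0% | 27.3-28.1% | -0.7 to +0.1 | 0.02-0.03 |

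Example, b = 0, c = 0.25, h = 4.3%: placebo 1 - 0.95 = 5.0%; prednisolone 1 - 0.957 × 0.975 = 6.7%; difference 1.7 points instead of 4.3.

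**The case against.** **The named endpoint is already protected.** Every AE gets a causality rating, and Protocol 12.4 reserves the possibly-related category for events that no other condition clearly explains. Synkinesis from the palsy would normally be rated unrelated. This stands. It confines the problem to the all-AE and all-SAE comparison, but that is the comparison for which SAP 8.7 states a test.

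**The documents never say that palsy sequelae are AEs.** True. It follows from mandatory wording without an exemption. The palsy is also graded separately by House-Brackmann, Sunnybrook and the SAQ, so sites may well not log it as an AE. SAP 8.2 also reports events before the first dose separately, which removes some early deepening. AE form instructions and the output shells lie outside the reviewed text and may settle the matter.

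**The size rests on assumptions.** This stands too. No logging rate is given, and the 20% versus 10% contrast describes non-recovery at 12 months, not early deepening. Without a benefit on recovery, this model gives no directional bias; palsy events only add noise.

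**The all-AE test is weak anyway.** With background AEs of 10-20% and no palsy events at all, the chance of a significant excess is only 0.15-0.38. So separating palsy events mainly corrects the estimated difference; it does not make the test powerful.

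**A stronger reading that fails.** A reader might infer that every non-recovered child becomes a disability SAE, giving 250 × 0.20 = 50 against 250 × 0.10 = 25, or half of that. The documents do not support such counts. Non-recovery is any House-Brackmann grade above 1, including mild residual weakness, and an unchanged palsy is not a new or worsened complaint.

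**Conclusion.** The point holds as a gap in SAP 8.7. Nothing in the recording rules keeps progression or new sequelae of the index palsy out of the AE and SAE counts, and the stated between-arm test uses those counts whole. If prednisolone improves recovery as assumed, the resulting bias runs against detecting drug harm.

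Its size is unknown. With a 4.3-5.4-point drug-caused excess, logging in a quarter of non-recovered children cuts the difference to between 1.4 and 2.8 points over the background rates shown, and logging in about 41-51% cancels it. These figures assume independent events, the SAP's recovery rates, and the protocol's side-effect rate read as an excess over placebo. A larger true excess is harder to cancel.

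A reader might go further and infer that the planned safety evaluation as a whole would hide prednisolone harm, or make the drug look safer. The documents do not support that: the related-AE endpoint is largely protected, a persisting palsy is not captured, and full reversal needs a logging share that nothing in the text suggests. The primary analysis is not affected.

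**What to change.** In SAP 8.7:
1. State a between-arm test for the named endpoint, AEs rated possibly or probably drug-related.
2. Compare AEs and SAEs twice: overall, and after excluding events coded as a sign, course or sequela of the index palsy. Do the coding blinded to arm and before database lock.
3. Show the excluded events in their own table by arm.

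Leave AE and SAE recording and expedited reporting as they are. If the AE form instructions or output shells already separate palsy events, a cross-reference in SAP 8.7 may replace the coding rule.

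The cost is one blinded pass through the AE terms and a few sentences in the SAP. The downside is that some coding decisions need judgement, for example tearing that could have another cause. The all-events comparison is kept for that reason.
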